3.1.4 Summary Statistics

Summary statistics will be presented by treatment group. Unless otherwise stated, continuous variables will be summarized by using the number of non-missing observations, arithmetic mean, standard deviation, median, minimum, and maximum values as descriptive statistics. Categorical variables will be summarized by using the frequency count and the percentage of patients in each category as descriptive statistics. 95% confidence intervals will be provided for categorical efficacy endpoints.

For time-to-event variables, the Kaplan-Meier method will be used to estimate the median time (weeks) and its 95% confidence interval.

3.1.5 Handling of Dropouts and Missing Data

In general, data will be analyzed and presented as observed and will not be imputed for the analysis of efficacy.

In case the start and end dates for AEs and concomitant medications/procedures are missing or incomplete, the missing component(s) will be assumed as the most conservative value possible. For example, AEs with missing start dates, but with stop dates either overlapping into the treatment period or missing, will be counted as treatment-emergent, taking the worst-case approach. When partial dates are present in the data, both a partial start date and/or a partial stop date will be evaluated to determine whether it can be conclusively established that the AE started prior to the start of study treatment or ended prior to the start of study treatment. If the above cannot be conclusively established based on the partial and/or present dates, then the AE will be considered as treatment-emergent. Actual data values as they appear in the original electronic case report forms (eCRFs) will be presented in the data listings.

All central CMV DNA PCR values will be used for the efficacy analyses and the local laboratory values will be listed. For the calculation of descriptive statistics of central CMV DNA results, below the lower limit of quantification (BLQ) values will be set to zero if result is reported as “< 102” with unit “IU/mL”. Missing data reported as “quality not sufficient” will not be imputed.

Changes in study visit schedules, missed or delayed visits, or patient discontinuations and the relationship to COVID-19 will be captured in the eCRFs.

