7 EFFICACY ASSESSMENTS

7.1 Primary Efficacy Endpoint

The primary efficacy endpoint is the incidence of CMV disease (CMV syndrome [see Appendix C for definition of CMV syndrome] or tissue-invasive CMV disease [see Appendix D for definitions of CMV disease]) or CMV viremia (defined as the detection of ≥ 250 IU/mL in plasma measured by PCR analysis in central laboratory or meets the local criteria for CMV viremia measured by PCR analysis or antigenemia testing) by Week 16.

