2.2.4 Sample Size Determination

A total sample size of approximately 108 patients is planned for the study, with a 1:1 randomization ratio for 6 mg/kg NPC-21 versus placebo and another 12 patients for high-level dose of 12 mg/kg NPC-21 (4:1:4 randomization ratio for 6 mg/kg NPC-21, 12 mg/kg NPC-21, or placebo). The sample size calculation is based on the modified Intent-to-Treat (mITT) Population from the first dose of NPC-21 through Week 16 for the occurrence of CMV disease (CMV syndrome or tissue-invasive CMV disease) or CMV viremia (defined as the detection of ≥ 250 IU/mL in plasma measured by PCR analysis in central laboratory or meets the local criteria for CMV viremia measured by PCR analysis or antigenemia testing) primary endpoint. Assuming an early discontinuation rate of 15%, approximately 48 patients each in the 6 mg/kg NPC-21 and placebo arms are needed with a 2-sided significance level of 0.05 and a power of 80% to detect a difference between NPC-21 at a predicted incidence rate of CMV disease (CMV syndrome or tissue-invasive CMV disease) or CMV viremia of 30% versus 60% for placebo. In addition, a sample size of 12 patients for the 12 mg/kg NPC-21 arm is considered adequate for the planned exposure-response analysis.

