2.3 Study Endpoints

2.3.1 Primary Efficacy Endpoint

The primary efficacy endpoint is the incidence of CMV disease (CMV syndrome [see Appendix C of protocol for definition of CMV syndrome] or tissue-invasive CMV disease [see Appendix D of protocol for definitions of CMV disease]) or CMV viremia (defined as the detection of ≥ 250 IU/mL in plasma measured by PCR analysis in central laboratory or meets the local criteria for CMV viremia measured by PCR analysis or antigenemia testing) by Week 16.

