3.4.1 Primary Efficacy Analysis

The proportion of patients with the occurrence of CMV disease (CMV syndrome [see Appendix C of the protocol for definition of CMV syndrome] or tissue-invasive CMV disease [see Appendix D of the protocol for definitions of CMV disease]) or CMV viremia (defined as the detection of ≥ 250 IU/mL in plasma measured by PCR analysis in central laboratory or meets the local criteria for CMV viremia measured by PCR analysis or antigenemia testing) by Week 16 will be summarized by treatment group.

The 2-sided 95% exact Clopper-Pearson confidence intervals of the proportions will be provided. For any two treatment groups, the proportion difference and 95% unstratified Miettinen-Nurminen (score) confidence limits will be presented.

Comparisons across placebo and 6 mg/kg NPC-21 treatment group will use logistic regression analysis with stratification factor of region (United States or Japan) as a covariate

Non-responders will include all patients who develop CMV disease or CMV viremia. In principle, patients who discontinue from the study prior to Week 16 in the absence of CMV disease or CMV viremia will be considered as non-responders. If warranted under special circumstances, a patient who discontinues from the study prior to Week 16 may be discussed with the medical expert to determine status as a responder or non-responder. If this occurs, the rationale for considering the patient as a responder will be finalized before database lock and documented in this SAP. Sensitivity analysis may be performed to assess the impact of these patients on analysis results.

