3.4.2.3 Time-to-Event Endpoints

The time-to-event endpoints include:

- Time to detectable CMV disease or CMV viremia by Week 28
- Time to detectable CMV disease by Week 28
- Time to detectable CMV viremia by Week 28

For each time-to-event endpoint, the count and proportion of patients experiencing event and censored will be summarized by treatment group. The Kaplan-Meier estimate of median time and Brookmeyer-Crowley 95% confidence intervals will be presented. Log-rank test will be used to test whether there is significant difference among groups.

The endpoints will be calculated as:

- Time to detectable CMV disease or CMV viremia by Week 28 (Weeks) = (Date of CMV disease or CMV viremia – first dose date of study drug + 1)/7.
- Time to detectable CMV disease by Week 28 (Weeks) = (Date of CMV disease – first dose date of study drug + 1)/7.
- Time to detectable CMV viremia by Week 28 (Weeks) = (Date of CMV viremia – first dose date of study drug + 1)/7.

If patients experience CMV disease or CMV viremia, the dates of entering Rescue Phase will be used to determine the date of CMV disease or CMV viremia and the patients will not be censored. Patients who do not experience CMV disease or CMV viremia will be censored at the latest CMV viremia assessments.

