3.4.3 Exploratory Analysis

As the exploratory analysis, incidence of CMV disease or CMV viremia by Week 16 assessed by Endpoint data reviewers will be analyzed using the method described in Section 3.4.1. In addition, the below endpoints will also be analyzed.

- Incidence of CMV disease or CMV viremia by Week 28
- Incidence of CMV disease by Week 28
- Incidence of CMV viremia by Week 28

In addition, the Endpoint data reviewer findings will be listed by-patient.

As the supportive analysis, only criteria using the detection of ≥ 250 IU/mL in plasma measured by PCR analysis in central laboratory will be considered for the analysis of primary efficacy endpoint in Section 3.4.1. Non-responders will include all patients who have central CMV DNA assessments ≥ 250 IU/mL by Week 16. Patients who discontinue from the study prior to Week 16 in the absence of central CMV DNA assessments ≥ 250 IU/mL will be considered as non-responders.

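### SAP 3.1.5 sends central PCR values to the efficacy analyses and local values to listings without exception; read literally, this conflicts with the primary endpoint, which counts local-criteria viremia as an event

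*SAP*

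**What the plan says.** SAP 3.1.5 (Handling of Dropouts and Missing Data) gives the data-source rule: "All central CMV DNA PCR values will be used for the efficacy analyses and the local laboratory values will be listed". The sentences after it cover results below the quantification limit and insufficient samples in the central CMV DNA data.

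The endpoint definitions give local results a different role. In SAP 3.4.1, viremia is central PCR at or above 250 IU/mL, or a result that "meets the local criteria for CMV viremia measured by PCR analysis or antigenemia testing". SAP 2.3.1 has the same two-part definition, as does protocol 7.1 ("meets the local criteria for CMV viremia measured by PCR analysis or antigenemia testing) by Week 16"). Protocol 10.2.1 and the sample size section (SAP 2.2.4) use the same composite.

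SAP 3.4.3 sets out a separate central-only analysis: "As the supportive analysis, only criteria using the detection of ≥ 250 IU/mL in plasma measured by PCR analysis in central laboratory will be considered". SAP 3.4.2.3, on the time-to-event endpoints, says that "the dates of entering Rescue Phase will be used to determine the date of CMV disease or CMV viremia".

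SAP section 4 lists the changes from the protocol. A move to central-only viremia is not among them. The addendum of 15 May 2023 revises non-responder rules and does not touch this point.

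**The concern.** One section says what local results are for (listing), and another makes them part of the primary event definition. A programmer who follows 3.1.5 to the letter and one who follows 3.4.1 to the letter could derive different primary event counts. Neither 3.4.1 nor 3.4.2.1 names the data that establish a local-criteria event, so nothing else in the SAP settles the matter.

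Three things are at stake.

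- **Direction of misclassification.** Local criteria are enough to enter the Rescue Phase (protocol 6.6), where anti-CMV agents are permitted. A patient rescued on a local result who never reaches 250 IU/mL centrally could be scored as a prophylaxis success.
- **A detection method.** Under protocol 7.3 the central laboratory performs PCR, and antigenemia testing is done only locally. The literal rule would remove antigenemia from the viremia limb altogether.
- **The planning basis.** The 60% and 30% rates in SAP 2.2.4 are for the composite that includes the local limb.

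**Working it through.** **1. The texts side by side**

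| Place | Role of local results |
|---|---|
| Protocol 7.1, 10.2.1 | Meeting local criteria is an event |
| SAP 2.3.1, 3.4.1 | Meeting local criteria is an event |
| SAP 2.2.4 | Sized on the composite with the local limb |
| SAP 3.4.3, supportive analysis | Not used; central PCR ≥250 IU/mL only |
| SAP 3.1.5 | Listed; central values go to the efficacy analyses |

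The supportive analysis would hardly be needed as a central-only check if the primary viremia limb were already central-only. It would then differ only by dropping the disease limb. Together with the silence of SAP section 4, this identifies 3.1.5 as the sentence out of line.

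**2. Which patients would be misclassified**

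On the literal reading, a patient with local-only viremia leaves the primary event count unless one of two other rules applies:

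- The patient also has CMV disease. Protocol Appendix C accepts antigenemia or nucleic acid testing for CMV syndrome and does not require the central laboratory.
- The patient discontinues before Week 16 and is a non-responder under 3.4.1.

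These backstops are weaker for the secondary viremia incidence endpoints at Weeks 16 and 28. The disease limb is not part of those endpoints, and addendum 2.1 removes the discontinuation rule from them.

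**3. The plan's own sample size**

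Inputs from SAP 2.2.4: 60% vs 30%, two-sided 0.05, power 80%, 1:1, 15% discontinuation, about 48 per arm.

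- Unpooled variance: n = (1.960 + 0.842)² × (0.6×0.4 + 0.3×0.7) / 0.30² = 7.849 × 0.45 / 0.09 = 39.2, so 40. Then 40/0.85 = 47.1, so 48, which matches.
- Pooled variance: 42, then 42/0.85 = 49.4, so 50.

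The sample size is not in dispute.

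**4. Illustration of size**

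The documents do not give the share f of events that meet only the local criteria. Assume the same f is lost in both arms, so the rates become 0.60(1−f) and 0.30(1−f). With p̄ the mean of the two rates p₁ and p₂, the pooled-formula power is

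Φ{ [ |p₁−p₂|√n − 1.960√(2p̄(1−p̄)) ] / √(p₁(1−p₁)+p₂(1−p₂)) }.

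| f (assumed) | Rates | Power, n = 48 | Power, n = 41 |
|---|---|---|---|
| 0 | 60% / 30% | 85% | 79% |
| 2% | 58.8% / 29.4% | 84% | 77% |
| 5% | 57% / 28.5% | 82% | 75% |
| 10% | 54% / 27% | 78% | 71% |
| 20% | 48% / 24% | 69% | 62% |
| 30% | 42% / 21% | 60% | 54% |

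The n = 48 column ignores dropout; n = 41 is 48 × 0.85 = 40.8, rounded up.

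Neither column is the primary analysis, which keeps discontinuers and counts them as non-responders. If 15% discontinued independently of events, the planned rates would be 0.15 + 0.85×0.60 = 66% and 0.15 + 0.85×0.30 = 40.5%. Power at 48 per arm would then be about 71% before any local event was lost. The table shows direction and scale only.

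**The case against.** The best defence is that 3.1.5 concerns numeric results. The rest of its paragraph deals with quantification limits and insufficient samples, whereas the local limb of the endpoint is a met/not-met status. Listing local values while counting a recorded local-criteria event is then coherent. The specific sections all point to local events being counted, and date and reason for Rescue Phase entry are recorded (protocol 6.6). This reading is plausible and probably what was meant. But the sentence refers to the efficacy analyses without limit, the next sentence turns separately to descriptive statistics of central results, and no section says that local events enter as a recorded status. The conflict in the wording stands.

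Other parts of the defence limit how far the point goes:

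- A reader might infer that 3.1.5 says only central values count. The word *only* is not there. The exclusion comes from the contrast between used and listed.
- A reader might infer that every local-only event disappears from every efficacy endpoint. The documents do not support that. Time-to-event dates come from Rescue Phase entry, which a local result can trigger, although 3.4.2.3 fixes the date and does not say which data establish the event. Some local-only patients also remain primary events through CMV disease or the discontinuation rule.
- A reader might infer a definite loss of power. The documents contain no figure for disagreement between local and central results. Central PCR is scheduled at each post-baseline visit that has local testing, so local-only events would mostly be discordant results, and the share could be small.

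**Conclusion.** The point holds as a conflict in the text. Taken literally, SAP 3.1.5 would give a primary event count that departs from the protocol definition, and it would do the same for the secondary incidence endpoints with a viremia limb. The time-to-event endpoints are less clearly affected. The weight of the other sections shows that local-criteria events are meant to count, so 3.1.5 is the sentence to change.

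The size of the effect is unknown. The power figures rest on an assumed local-only share, equal proportional loss in both arms, no rescue of events through the disease or discontinuation rules, and a two-proportion formula rather than the planned logistic regression. The conclusion does not depend on them. The documents do not show that the sponsor's analysis in fact dropped local events, and that should not be inferred.

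This should be corrected: it bears on how the primary endpoint is derived, and the correction is small.

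**What to change.** Reword the sentence in SAP 3.1.5 along these lines:

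> Quantitative CMV DNA summaries and the supportive analysis in 3.4.3 use central values only. Viremia events for the primary, secondary incidence and time-to-event endpoints use central PCR ≥250 IU/mL or local criteria as defined in 3.4.1.

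Then name, in 3.4.1 and 3.4.2, the data source that identifies a local-criteria event: the local laboratory results, the recorded reason for Rescue Phase entry, or both. If both, say which prevails when they disagree.

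The cost is one SAP sentence plus the data-source statement, with no new data. The SAP was finalized on 29 March 2023 and the database was locked on 30 March 2023 (addendum section 1), so the change has to be documented as a post-lock clarification. It should say that it restores the protocol definition.

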10.2 Statistical Methods

10.2.1 Analysis of Efficacy

The mITT Population will be used for all efficacy analyses.

The primary efficacy endpoint will be the proportion of patients with the occurrence of CMV disease (CMV syndrome [see Appendix C for definition of CMV syndrome] or tissue-invasive CMV disease [see Appendix D for definitions of CMV disease]) or CMV viremia (defined as the detection of ≥ 250 IU/mL in plasma measured by PCR analysis in central laboratory or meets the local criteria for CMV viremia measured by PCR analysis or antigenemia testing) by Week 16. Non-responders will include all patients who develop CMV disease or CMV viremia. In principle, patients who discontinue from the study prior to Week 16 in the absence of CMV disease or CMV viremia will be considered as non-responders. If warranted under special circumstances, a patient who discontinues from the study prior to Week 16 may be discussed with the medical expert to determine status as a responder or non-responder. If this occurs, the rationale for considering the patient as a responder will be finalized before database lock and documented in the Statistical Analysis Plan. Sensitivity analysis may be performed to assess the impact of these patients on analysis results.

The primary efficacy endpoint will be summarized by treatment group and compared across placebo and the 6 mg/kg NPC-21 treatment group using a logistic regression analysis with stratification factor of region (United States or Japan) as a covariate.

Other efficacy endpoints will be summarized descriptively by treatment group using the mITT Population.

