3.4.2.2 Continuous Endpoints

Descriptive statistics will be presented by treatment group for the continuous endpoints as below:

- Amount of CMV DNA by PCR analyzed by the central laboratory
 - Descriptive statistics will be provided for amount of CMV DNA (IU/mL) at each scheduled visit and changes from baseline will be presented as well.
- Duration of anti-CMV therapy during the Rescue Phase
- Duration of the detection of CMV DNA ≥ 250 IU/mL in plasma measured by PCR analysis in central laboratory
- Changes in EQ-5D-5L score from Baseline to Weeks 16 and 28
 - Counts and percentages of patients with each of five response levels in each domain will be presented by treatment and visit.
 - Changes from baseline for total health status will be presented as well.

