3.5 Analysis of Pharmacokinetic

Serum concentrations of NPC-21 will be summarized using descriptive statistics. Geometric mean and geometric coefficient of variation will also be provided. For the calculation of descriptive statistics, BLQ values will be set to zero and missing data will not be imputed. 2-hour post-dose samples collected outside the sampling window of 2 hours +/- 30 minutes after infusion start may be excluded from the calculation of descriptive statistics. Plots of mean concentrations of plasma NPC-21 versus time will be generated for each dose group and scheduled visit.

In addition, analysis of the concentration data as part of population-PK modeling will be described in a separate PK Analysis Plan and reported separately.

The PK listing will be provided.

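### The secondary endpoint 'amount of CMV DNA' is summarised only in raw IU/mL; adding the percentage below quantification and a log10 summary would make the table informative

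*SAP*

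**What the plan says.** The amount of CMV DNA by central PCR is a named secondary endpoint (Protocol 7.2; SAP 2.3.2). SAP 3.4.2.2 gives its analysis: "Descriptive statistics will be provided for amount of CMV DNA (IU/mL) at each scheduled visit and changes from baseline will be presented as well". The general rule in SAP 3.1.4 supplies the statistics, which are the number of observations and the "arithmetic mean, standard deviation, median, minimum, and maximum values as descriptive statistics". SAP 3.1.5 says that, for descriptive statistics of central CMV DNA, "below the lower limit of quantification (BLQ) values will be set to zero" if the laboratory reports < 102 IU/mL.

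The endpoint carries no test. Protocol 10.2.1 says: "Other efficacy endpoints will be summarized descriptively by treatment group using the mITT Population". SAP 3.4.2.2 opens with: "Descriptive statistics will be presented by treatment group for the continuous endpoints as below".

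Neither the SAP nor its addendum plans a log10 or geometric summary of CMV DNA. SAP 3.5 does plan one for serum NPC-21 concentration: "Geometric mean and geometric coefficient of variation will also be provided".

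**The concern.** Viral load commonly spans orders of magnitude. On the raw scale the mean and SD of such data reflect the few largest values, so the arm means can differ, even in direction, because of one or two patients. The median resists those values, but it is exactly zero whenever more than half of an arm is below quantification (BLQ) at a visit. Patients with viremia by local criteria at Screening are excluded (Protocol 4.2, criterion 3). Most baselines are therefore probably BLQ, and raw change from baseline would largely repeat the raw value.

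At stake is whether the table for a named secondary endpoint can say anything about the magnitude of viral load. No test or decision depends on it.

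**Working it through.** **Inputs from the documents.** The BLQ threshold is 102 IU/mL (SAP 3.1.5). Arm sizes come from SAP 2.2.4: "approximately 48 patients each in the 6 mg/kg NPC-21 and placebo arms are needed with a 2-sided significance level of 0.05", with 12 at 12 mg/kg. The documents give no SD, effect size, power or distribution for CMV DNA.

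**The plan's own figure.** The arm size reproduces with unpooled variance: (1.960 + 0.842)² × (0.3 × 0.7 + 0.6 × 0.4) / 0.3² = 39.24, rounded up to 40; 40 / (1 − 0.15) = 47.1, rounded up to 48. Allocation: 108 × 4/9 = 48 and 108/9 = 12.

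**One high value.** Suppose one patient is at 100,000 IU/mL and all others in the arm are BLQ.
- Arm of 48: mean 100,000/48 = 2,083 IU/mL; median 0.
- Arm of 12: mean 100,000/12 = 8,333 IU/mL; median 0.

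**When the median is zero.** With 48 patients observed, the median is zero if 23 or fewer are quantifiable. From the binomial distribution:
- 30% quantifiable: probability 0.997.
- 60% quantifiable: probability 0.06.

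**Simulation of one visit (assumed loads).** There were 48 patients per arm and 20,000 runs. Quantifiable loads were log-normal and floored at 102: log10 mean 3 with log10 SD 0.7, 1.0 or 1.3, and log10 mean 3.5 with SD 1.0. The proportion quantifiable was 10%, 30% or 60% on placebo and half that on active. The central case is log10 mean 3, SD 1.0, with 30% versus 15% quantifiable. For log10, the share is of the arm's excess over the 51 IU/mL floor.

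| Measure | Raw, BLQ = 0 | Log10, BLQ = 51 |
|---|---|---|
| Share from the two largest placebo values (median over runs), central | 73% | 28% |
| Same, all scenarios | 44% to 96% | 13% to 69% |
| Mean higher on active than placebo, central | 27% | 7% |
| Same, all scenarios | 16% to 32% | 0.6% to 22% |

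**What the zero rule contributes on the raw scale.** Replacing 0 by a value s changes the difference in means (placebo minus active) by (0.70 − 0.85) × s in the central case. For s = 51 that is −7.7 IU/mL, and for s = 102 it is −15.3. The simulated differences agree: 2,013 with zero, 2,006 with 51 and 1,998 with 102. No arm mean can move by more than 102 IU/mL.

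**What the substitute contributes on log10.** Log10(0) is undefined, so some substitute is needed. The simulated central-case differences are 0.47 (1 IU/mL), 0.21 (51) and 0.16 (102). The steps follow from 0.15 × the log ratio of the substitutes:
- 0.15 × log10(51) = 0.15 × 1.708 = 0.26.
- 0.15 × log10(2) = 0.15 × 0.301 = 0.045.

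**The case against.** The strongest reply is that this is a presentation choice for a descriptive table. Viremia is covered elsewhere: incidence by Weeks 16 and 28 (SAP 3.4.2.1), time to viremia (3.4.2.3), duration of CMV DNA at or above 250 IU/mL (3.4.2.2), and a supportive analysis on the central threshold alone (3.4.3). The planned table prints the maximum, so a reader would see an outlier. Weekly sampling to Week 24, with rescue available from 250 IU/mL, may also shorten the upper tail. All of this stands and limits the size of the point. It does not make the raw mean or a zero median informative about magnitude.

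The log10 summary has its own weakness. With BLQ set to 51, the one-high-value example in 48 patients gives a geometric mean of 10^((47 × log10 51 + 5)/48), about 60 IU/mL, which nearly hides the 100,000. If most baselines are BLQ, log10 change mainly measures distance from the substitute. This also stands, and is why the raw table should stay and the BLQ percentage should sit beside the log10 summary.

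A reader might draw four stronger conclusions that the documents do not support.
- *The zero rule causes the outlier problem.* It does not; its effect on an arm mean is at most 102 IU/mL.
- *One or two patients decide the result.* Both documents make the endpoint descriptive, with no test.
- *The zero rule scores detectable virus as none.* SAP 3.1.5 does not say whether < 102 includes samples with no target detected. If it does, substituting 51 assigns virus to negative patients.
- *The coefficient of variation will be 14 or more.* That is the population value for a pure log-normal with log10 SD 1.0. In 48 non-negative values the sample figure cannot exceed √48 = 6.9.

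**Conclusion.** The point holds as a cheap improvement to a descriptive table. Under the assumed skewed loads, the raw mean points the wrong way in 16% to 32% of simulated visits, against 0.6% to 22% on log10 with BLQ set to 51. The advantage is large when many patients are quantifiable and modest when few are. The planned median is almost always zero at visits where 30% or fewer are quantifiable, but usually not at 60%.

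These sizes rest on log-normal loads and assumed proportions quantifiable, since the documents give neither. The raw scale is the source of the instability. The zero rule matters because it leaves the log scale undefined, and any substitute affects the log10 difference (0.16 to 0.47 in the central case). It would go too far to infer that the trial's evidence on viremia is unsound, or that a log10 summary settles the question without a sensitivity check.

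**What to change.** Keep the planned IU/mL table. For each visit and arm, add:
- the number and percentage BLQ (< 102 IU/mL) and at or above 250 IU/mL, neither of which needs a substitute;
- a descriptive log10 IU/mL summary (geometric mean, median, quartiles, log10 change from baseline) with < 102 set to 51 IU/mL, repeated with one alternative such as 102 IU/mL.

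State whether < 102 includes samples with no target detected. Do not add a geometric mean ratio with a confidence interval, or else label it exploratory: it depends on the substitute, and SAP 3.1.5 uses all central values, including those after rescue therapy has begun.

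The cost is SAP wording and programming, with no added patients or samples. The downside is a conventional substitute, which the BLQ percentages and the sensitivity value make visible. The SAP was final on 29 March 2023 and the database was locked on 30 March 2023, so the tables must be labelled post hoc. The addendum of 15 May 2023, which already revises secondary analyses after lock, shows a route for documenting them.
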